The protocol, informed consent form, recruitment materials, and all participant materials were submitted to the University of Pittsburgh's Institutional Review Board (IRB) for review and approval. The protocol and consent form were approved before enrolling any participants. Any amendments to the protocol will be submitted to the IRB for review and approval prior to implementing the changes in the study. Additionally, all changes to the consent form will be reviewed and approved by the IRB; a determination will be made as to whether a new consent must be obtained from participants who provided consent using a previously approved consent form.

[figure not shown]
1 PROTOCOL SUMMARY

1.1 SYNOPSIS

Title:	Sleep GOALS (Goal-focused Online Access to Lifestyle Support)
Study Description:	This study will use a single-blind, parallel-arm, randomized controlled trial design. Participants will be randomized at a 1:1 ratio to the Sleep GOALS intervention or education control group. We will measure indicators of study feasibility and acceptability to identify and refine factors related to the conduct of the planned larger trial and intervention content and estimate the change in secondary outcomes. See Schema and Schedule of Activities, Sections 1.2 and 1.3 , respectively.
Objectives:	Primary Objective: To determine the feasibility and acceptability of Sleep GOALS Secondary Objectives: To determine the preliminary efficacy of Sleep GOALS
Endpoints:	Primary Endpoint: The intervention's feasibility (i.e., recruitment, enrollment, attrition rates, intervention engagement) and acceptability (i.e., participant ratings of the intervention delivery, curricula, action plans, intervention platform, and coaching) Secondary Endpoint: Weight loss and retention of pregnancy and postpartum weight gain
Study Population:	40 individuals from Allegheny County who are between 3±1 and 6±1 postpartum, has a body mass index ≥ 25 kg/m ² , self-report less than 150 minutes of moderate-to-vigorous intensity physical activity (e.g., brisk walk) per week, self-report at least one sleep disturbance, and has Internet access.
Phase:	N/A
Description of Sites/Facilities	Baseline and post-intervention assessments will occur at the Perinatal Health Behavior (PHB) Lab on the University of Pittsburgh's campus, [name]. Post-intervention semi-structured interviews will take place in the PHB lab or Zoom, at the participant's preference. Baseline assessments will occur prior to randomization (Week 0), and post-intervention assessments will occur immediately following completion of the 16-week intervention period (Week 16)
Enrolling Participants:	

Description of Study Intervention:	16-week online intervention that includes 1) informational videos that provide strategies to improve sleep, diet, and physical activity to achieve weight loss, 2) a lifestyle coach, 3) a commercial activity tracker (e.g., Fitbit Charge 5) to monitor sleep and physical activity, and 4) wireless scale (e.g., Aria) to monitor weight.
Study Duration:	The study will last 18 months from the time it opens enrollment until the data analysis is complete.
Participant Duration:	The participants will complete all study visits in 18 to 20 weeks.

1.2 SCHEMA

1.3 SCHEDULE OF ACTIVITIES (SOA)

Procedures	Screening, Day -7 to -1	Enrollment/Baseline, Day -7 to -1	Day 1	Final Assessment, Day 112+8
Eligibility determination	X			
Informed consent		X		
Randomization		X		
Administer the intervention			X-----X	
Outcome Assessment				
Feasibility indicators		X		
Acceptability indicators			X-----X	
Height and Weight	X	X		X
Descriptive characteristics				
Demographics	X	X		
Infant Feeding and Behavior		X		X
Mental Wellness		X		X

Treatment Expectations		X		
Weight Goals		X		
Social Support		X		X
Social Determinants of Health		X		
Health Behaviors				
Physical activity	X	X		X
Diet		X		X
Sleep	X	X		X

2 INTRODUCTION

2.1 STUDY RATIONALE

Pilot testing will help us identify and refine factors related to the conduct of the planned larger, definitive trial and estimate the change in secondary outcomes.

2.2 BACKGROUND

- Postpartum weight retention and maternal obesity are associated with short- and long-term maternal morbidity and mortality risk.
- The US Preventive Services Task Force recommends that clinicians offer or refer individuals with obesity to an intensive behavioral weight-loss intervention that addresses diet and physical activity
- Most weight-loss interventions among postpartum individuals have followed these recommendations but have produced only modest effects and had substantial heterogeneity.
- Sleep is independently associated with obesity and weight gain and bi-directionally associated with diet and physical activity. However, diet and physical activity interventions are rarely integrated with sleep interventions.
- Integrating sleep interventions with diet and physical activity may enhance weight loss among postpartum individuals.

2.3 RISK/BENEFIT ASSESSMENT

2.3.1 KNOWN POTENTIAL RISKS

We categorize the frequency of possible risk using the following categories: likely (occurs in >25% of people), common (occurs in 10-25% of people), infrequent (occurs in 1-10% of people), and rare (occurs in <1% of people). We will monitor the risk related to the intervention and data collection.

Intervention-Related Risk:

- The recommended physical activity may cause muscle soreness or fatigue (likely). There is the possibility that the following occurs during exercise: injury of a joint or muscle (common), broken bones (rare), falls from exercise equipment (infrequent). There is also the possibility of aggravating pre-existing problems (common), shortness of breath (common), abnormal blood pressure (common), fainting (rare), disorders of heart rhythm (rare), heart attack, stroke, or even death (rare).
- The recommended weight loss may cause constipation (common) and dizziness upon standing (common). Rapid weight loss increases the chances of developing or enlarging gallstones (rare). Other risks include hypoglycemia (infrequent), light-headedness or weakness (common), and hunger (likely).
- Wearing the wrist-worn activity monitor may cause some discomfort in the form of skin irritation (infrequent).

Data Collection Related Risk:

- The potential risks of participating in this study include discomfort (rare) from answering questions, disclosure of postpartum depression or child neglect/abuse (infrequent), and breach of confidentiality (rare).

2.3.2 KNOWN POTENTIAL BENEFITS

Participants enrolled in both intervention arms of the study may benefit from losing weight and learning strategies to improve weight-related behaviors, i.e., dietary intake, physical activity, and sleep. Participants enrolled in the Sleep GOALS intervention arm may benefit from having a lifestyle coach who can provide them with tailored information to support behavior change. Society may benefit from the study information because it will inform an intervention to improve maternal weight and health postpartum.

2.3.3 ASSESSMENT OF POTENTIAL RISKS AND BENEFITS

Postpartum weight retention (PWR) predicts weight gain and obesity development in women. PWR increases the risk of adverse maternal outcomes (e.g., preeclampsia, gestational diabetes) in subsequent pregnancies, additional weight gain, and long-term cardiovascular disease (CVD) development. The postpartum period is critical for engaging individuals in weight-loss interventions to prevent PWR and future CVD morbidity and mortality. Most weight-loss interventions among postpartum individuals have addressed diet and physical activity and have produced only modest effects. Poor sleep, common during the postpartum period, has rarely been addressed in standard weight loss interventions. Interventions that address poor sleep may enhance the efficacy of standard weight-loss interventions. The knowledge gained in this study will inform the refinement of a weight loss intervention for postpartum individuals that addresses diet, physical activity, and sleep. Iterative development of the intervention, which incorporates user feedback at various stages, is likely to increase the intervention's feasibility, acceptability, and efficacy. Participants will learn strategies for improving their sleep, diet, and physical activity and self-select the activities that fit their circumstances. Given the minimal risks of the proposed assessments, the potential benefits to the individuals and society greatly outweigh the risks of conducting the proposed research.

3 OBJECTIVES AND ENDPOINTS

Primary Outcomes: The primary outcomes are feasibility and acceptability factors relevant to conducting a subsequent efficacy trial, including the feasibility of recruitment, retention, and engagement (Table 5). To determine acceptability, we will ask participants to complete a modified Acceptability and Feasibility Questionnaire¹ post-intervention. The questionnaire asks participants to provide answers on a 5-point scale (1=*don't agree at all* to 5=*totally agree*) to 39 items about the intervention delivery (e.g., logical, understandable), curricula (e.g., was it logical, relevant, instructive), action plans (e.g., useful, easy to follow), and intervention platform (e.g., user friendly). We will also ask about the coaches' effectiveness, overall satisfaction with the intervention, and the likelihood they would recommend it to a friend. Items with an average score of <4 will be flagged for refinement.

We will then conduct 60-minute semi-structured interviews with participants and coaches. The interviews will take place in person (PHB lab) or by video chat at the participant's preference. We will ask participants whether the content was understandable, the recommendations achievable, and what adaptations are necessary to improve low-scoring items. We will ask the lifestyle coach to discuss their experience and provide suggestions for improving the delivery of the material and their workflow. All interviews will be audio-recorded and transcribed by Qual EASE for qualitative analysis. The feedback will be used to refine the intervention's content delivery, coach's workflow, and training manual. Participants will receive \$50 after each assessments and intervention participants will receive a \$25 honorarium for completing the post-intervention interview.

Secondary Outcomes: *Weight* will be measured with a digital scale, with the participant wearing light clothing and no shoes at baseline and post-intervention. We will estimate PWR as the difference in measured weight at post-intervention and self-reported pre-pregnancy weight.

Analysis Plan: The primary study objective is to assess the feasibility and acceptability of Sleep GOALS. We will assess the feasibility of the intervention by estimating rates of recruitment, retention, and engagement (i.e., weekly logins; modules completed; daily self-monitoring of diet, physical activity, and sleep; weekly monitoring of weight using point estimates (means or sample proportions) and 95% confidence intervals). We will assess acceptability by estimating satisfaction rates on various intervention components (≥ 4 Acceptability and Feasibility Questionnaire). Our benchmarks for feasibility are similar to those used in the original GOALS Lifestyle intervention. We will use a benchmark of 80% for all feasibility and acceptability measures. To assess the intervention's preliminary efficacy, we will calculate point estimates and confidence intervals for change in weight and PWR. We chose these weight measures as our secondary outcomes since they will be the primary outcome in the future R01. However, we will also explore changes in our proposed behavioral mediators, sleep, diet, and physical activity to inform power calculations for a fully powered study.

We will conduct an exploratory analysis to determine how potential covariates (e.g., parity, breastfeeding status, postpartum depression, race/ethnicity, relationship status, and employment status) impact the intervention's feasibility, acceptability, and preliminary efficacy. For example, in some studies, breastfeeding is associated with longer nocturnal sleep²⁻⁴, but shorter nocturnal sleep in other studies.⁵ Collecting data on breastfeeding and other covariates will provide preliminary data on how it impacts the intervention.

Domain	Measure, Method of Assessment	Benchmarks for Success
Feasibility (Primary Outcome)		
Recruitment/Enrollment	Total sample	40 participants in 12 months
	Demographics of sample	$\geq 30\%$ ethnic minority
Retention	Attrition Rates	$\leq 20\%$ loss to follow-up
Engagement	Modules completed	≥ 14 (~80%) modules completed within 16 weeks
	Weekly self-monitoring of diet, sleep, and physical activity weekly	≥ 14 (~80%) weeks, ≥ 1 day of monitoring
	Weekly weigh-ins	≥ 14 (~80%) weeks, ≥ 1 day of weigh-ins
	Total time logged in	
Acceptability (Primary Outcome)		
Acceptability	Acceptability of the intervention delivery; behavior change curricula; action plan; intervention platform	$\geq 80\%$ agree or totally agree with each
Preliminary efficacy (Secondary Outcome)		
Weight	Weight change	$> 5\%$ weight loss
	Postpartum weight retention	< 5 kg of weight retention
The primary endpoints will inform factors related to the conduct of the study (i.e., feasibility) and the intervention content and delivery (i.e., acceptability) of the planned larger definitive efficacy trial. The secondary outcomes will provide estimates of the intervention's effects on the primary outcome of the planned larger definitive efficacy trial		

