4.3 JUSTIFICATION FOR DOSE

Over the 16-week intervention, participants will have access to 16 (~20-minute) information videos, made available weekly. The intervention content will be delivered via a secure online platform. Participants can access the intervention content at their convenience, which increases the intervention's feasibility for postpartum people with small children. The intervention 16-week are similar in dose to other weight loss interventions.

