9.4.2 ANALYSIS OF THE PRIMARY EFFICACY ENDPOINT(S)

The primary endpoints are the feasibility and acceptability of Sleep GOALS. We will assess the feasibility of the intervention by estimating rates of recruitment, retention, and engagement (i.e., weekly logins; modules completed; daily self-monitoring of diet, physical activity, and sleep; weekly monitoring of weight using point estimates (means or sample proportions) and 95% confidence intervals). We will assess acceptability by estimating rates of satisfaction on various components of the intervention (≥ 4 Acceptability and Feasibility Questionnaire). Our benchmarks for feasibility are similar to those used in the original GOALS Lifestyle intervention. We will use a benchmark of 80% for all feasibility and acceptability measures. To assess the intervention's preliminary efficacy, we will calculate point estimates and confidence intervals for change in weight and PWR. We chose these weight measures as our secondary outcomes since they will be the primary outcome in the future R01. However, we will also explore changes in our proposed behavioral mediators, sleep, diet, and physical activity to inform power calculations for a fully powered study.

We will conduct an exploratory analysis to determine how potential covariates (e.g., parity, breastfeeding

status, postpartum depression, race/ethnicity, relationship status, and employment status) impact the intervention's feasibility, acceptability, and preliminary efficacy. For example, in some studies, breastfeeding is associated with longer nocturnal sleep, but shorter nocturnal sleep in other studies. Collecting data on breastfeeding and other covariates will provide preliminary data on how it impacts the intervention.

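### The engagement cut-off of 14 is labelled about 80%, but 14 of 16 is 87.5%, and self-monitoring is daily in the analysis text but weekly in the benchmark table.

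*Combined protocol and SAP*

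**What the plan says.** The benchmark table in Section 3 gives three engagement cut-offs, each a minimum and each carrying the same percentage:

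- Modules: "14 (~80%) modules completed within 16 weeks".
- Self-monitoring, a measure named "Weekly self-monitoring of diet, sleep, and physical activity weekly": "14 (~80%) weeks, ≥ 1 day of monitoring".
- Weigh-ins: "14 (~80%) weeks, ≥ 1 day of weigh-ins".

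The analysis plan in Section 3 adds: "We will use a benchmark of 80% for all feasibility and acceptability measures". Section 9.4.2 repeats that statement.

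On the denominator, Section 4.3 says that "participants will have access to 16 (~20-minute) information videos, made available weekly". Section 6.1.1 also lists 16 videos and fixes the intervention at 16 weeks for every participant.

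On self-monitoring, the analysis text in Sections 3 and 9.4.2 lists "daily self-monitoring of diet, physical activity, and sleep" among the engagement measures. The same sentence describes weight monitoring as weekly.

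**The concern.** Two things do not fit together. First, the percentage printed beside 14 does not match 14 out of the 16 modules or weeks that the plan provides, so the text and the table set different pass marks. Second, the analysis text and the table describe self-monitoring at different frequencies.

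Engagement is part of the primary outcome, and Section 3 says that the primary endpoints will inform the definitive trial. Section 9.1 rules out formal hypothesis testing, so these benchmarks are the only stated success criteria for engagement. If the pass mark can be read in two ways, the choice could be made after the results are known.

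**Working it through.** **Inputs.** Cut-off 14 and label of about 80%: Section 3 table. Number of videos, 16: Sections 4.3 and 6.1.1. Number of weeks, 16: Section 6.1.1, and the module row itself. Benchmark 80%: Sections 3 and 9.4.2.

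**Step 1: try to reproduce the label** (cut-off divided by denominator).

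- 14/16 = 0.875, or 87.5%. This is 7.5 percentage points above the label.
- Working backwards, 14/0.80 = 17.5, so the label would suit 17 units (14/17 = 82.4%) or 18 units (14/18 = 77.8%).
- The documents give neither 17 nor 18 as the number of modules or intervention weeks. The 18 to 20 weeks in the synopsis is the time to complete all study visits.

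The label is not reproduced.

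**Step 2: find the cut-off that 80% implies.**

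- 0.80 × 16 = 12.8, so the smallest whole number at or above 80% is 13.
- 13/16 = 81.25%, and 12/16 = 75%.

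The approximation sign does not explain the choice of 14, because 13 is 1.25 points from 80% and 14 is 7.5 points from it.

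**Step 3: what one unit can change.** Let X be the number of modules (or qualifying weeks) out of 16 for one participant. Assume, for illustration, that units are independent with the same probability p, so X is Binomial(16, p).

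| p | P(X ≥ 14) | P(X ≥ 13) |
|---|---|---|
| 0.75 | 19.7% | 40.5% |
| 0.80 | 35.2% | 59.8% |
| 0.85 | 56.1% | 79.0% |
| 0.90 | 78.9% | 93.2% |
| 0.95 | 95.7% | 99.3% |

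At p = 0.80 the difference is 59.8 − 35.2 = 24.6 points, which is P(X = 13).

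**Step 4: relax independence.** Engagement probably clusters within people; Sections 5.4 and 6.3 plan for participants who are inactive for two weeks in a row. Take X as beta-binomial with mean 0.80 and within-participant correlation ρ, with beta parameters 0.80(1−ρ)/ρ and 0.20(1−ρ)/ρ. The values of ρ are assumptions.

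| ρ | P(X ≥ 14) | P(X ≥ 13) | Gap (points) |
|---|---|---|---|
| 0 | 35.2% | 59.8% | 24.6 |
| 0.1 | 46.5% | 61.1% | 14.6 |
| 0.3 | 57.5% | 65.3% | 7.8 |
| 0.5 | 65.1% | 69.6% | 4.5 |

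The gap persists but shrinks as clustering increases.

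**Step 5: compare the self-monitoring definitions.** The analysis text names a daily measure. The table names a weekly one, and a week counts with a minimum of "1 day of monitoring". For weight, text and table are both weekly, so the mismatch is confined to diet, physical activity and sleep.

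**The case against.** The strongest reply is that the table can be applied as it stands. The integer 14 is the same in all three rows, and the percentage beside it is only an approximate gloss. The study is a pilot with descriptive statistics, no hypothesis tests and no stop/go rule, and the reported estimates would show 81% or 87% whatever the label says. That stands, and it limits the severity. It does not remove the conflict with the 80% statement, because 13 of 16 passes one and fails the other.

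A second reply is that the 80% may refer to the share of participants who reach the cut-off, in which case 14 could be a deliberate per-participant rule. The documents allow this, since they permit means or sample proportions and do not say which is judged against 14. The table nevertheless attaches the percentage to modules and weeks, where it is wrong. This reply shows that the unit of analysis also has to be stated.

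A third is that equating modules with videos is an inference. It is a reasonable one, given 16 videos released weekly, and the two week-based rows do not need it. Section 4.1 leaves the length to the results of Aim 1, but Section 6.1.1 settles it at 16 weeks.

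A reader might also go further on self-monitoring. One day in each of 14 weeks can be as few as 14 of 112 days (12.5%), and one might infer that this too disproves the label, or that the plan requires 80% of days (0.80 × 112 = 89.6, so 90) and differs from its own table about sixfold. The documents do not support either inference. In that row the percentage qualifies weeks, and no section sets a benchmark in days. What they show is a measure called daily in one place and weekly in another.

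**Conclusion.** The point holds as a should-fix. With the plan's own denominator of 16, the cut-off of 14 is 87.5%, and 80% corresponds to 13 (81.25%). This affects all three labelled engagement rows; it rests only on simple division and, for the module row, on reading modules as the weekly videos. Its practical effect cannot be fixed from the documents. If 80% of modules are completed on average, the share of participants who reach the cut-off is 24.6 points lower with 14 than with 13 under independence, and 4.5 to 14.6 points lower for within-participant correlations from 0.5 to 0.1. The daily versus weekly mismatch is real, but it is a matter of definition, and no size should be attached to it.

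A reader might infer that a cohort averaging between 13 and 14 modules would necessarily be declared a failure. That follows only if the cohort mean is what is compared with 14, which the plan does not say.

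**What to change.** Before engagement data are examined:

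1. State the denominator in the table: 16 modules and 16 weeks.
2. Either change the three cut-offs to 13 or more (81.25%), or keep 14, label it 87.5%, and exempt these measures from the all-measures 80% statement in Sections 3 and 9.4.2.
3. State whether the cut-off applies to each participant, with the proportion reaching it compared with 80%, or to the cohort mean.
4. Use one definition of self-monitoring throughout. The simplest course is to carry the table's weekly rule into the analysis text of Sections 3 and 9.4.2. Reporting the percentage of days monitored as well is optional.

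The cost is an edit to one table and two paragraphs. No new data are needed, because Section 6.3 says that the platform already tracks lessons viewed and self-monitoring. The sample size is unaffected.

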5.1 INCLUSION CRITERIA

To be eligible to participate in this study, an individual must meet all of the following criteria:

1. Provision of signed and dated informed consent form,
2. Stated willingness to comply with all study procedures and availability for the duration of the study,
3. Primiparous, singleton pregnancy,
4. Between 3 \pm 1 and 6 \pm 1 months postpartum,
5. Has a body mass index $>$ 25 kg/m²,
6. Physically inactive, defined as self-reporting $<$ 150 minutes/week of moderate-to-vigorous intensity physical activity,
7. Endorse $>$ 1 indicator of poor sleep health based on the RU_SATED questionnaire, and
8. Has smartphone and home Internet access

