5.2 EXCLUSION CRITERIA

An individual who meets any of the following criteria will be excluded from participation in this study:

1. current use of medications that affect weight (see Appendix 1),
2. currently pregnant or plan to become pregnant during the study period (18 weeks), and
3. participating in another weight loss intervention.

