8 STUDY ASSESSMENTS AND PROCEDURES

8.1 PRELIMINARY EFFICACY AND COVARIATE ASSESSMENTS

Assessments will be conducted at baseline (Week 0) prior to randomization and immediately after completion of the intervention (Week 16). Assessments will be conducted by a research team member in the PHB lab. Assessments should take 1-2 hours to complete. Participants will receive pre-visit instructions 3 days before their scheduled in-person visits. Assessments will consist of the following:

- Height, weight & waist circumference: Height will be measured with a stadiometer at study enrollment (T0). Weight will be measured using a calibrated digital scale. Women will be measured in street clothes without shoes.
- Demographic information: Age, race, ethnicity, income, educational background, employment status, health insurance status, marital status, family composition (e.g., number of adults and children in the household), smoking status, and current alcohol use.
- Mental wellness: Participants will complete the Edinburgh Postnatal Depression Scale to measure the frequency of depressive symptoms. The Perceived Stress Scale will be used to measure perceived stress.
- Infant sleep and eating: The Brief Infant Sleep Questionnaire - Revised (BISQ) Short Form will be used to assess infant sleep patterns. The infant feeding questionnaire to assessing infant eating patterns.
- Social determinants of health: The Barkin Index of Maternal Functioning (BIMF) is a 20-item self-report measure that was designed to assess overall functioning in the context of new motherhood. The EveryONE project social determinants of health screener to identify the social needs of participants.
- Social support: The RAND social support survey helps identify the types of support available to participants.
- Diet: The study will utilize the Automated Self-Administered 24-hour (ASA24) Dietary Recall System to collect information about what participants ate in the prior 24 hours
- Physical activity and sleep: Following the in-person visit, we will give participants an Actigraph Link, which is a research-grade activity monitor, to wear on their wrist for 7

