9.3 POPULATIONS FOR ANALYSES

For primary outcomes related to feasibility, we will include all randomized participants. For primary outcomes related to intervention acceptability, we will include all participants randomized to the Sleep GOALS intervention. For secondary outcomes, we will include all randomized participants (i.e., intention-to-treat)

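### The benchmark of less than 5 kg retained weight is a Week 16 level with no entry minimum, so it can be met at enrolment or after weight gain and is not by itself evidence of preliminary efficacy

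*Combined protocol and SAP*

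**What the plan says.** - **Benchmark.** In the Section 3 table, under preliminary efficacy, the success benchmark for postpartum weight retention (PWR) is "< 5 kg of weight retention". The row does not say whether this applies to each participant or to a group mean, or to which arm. The companion benchmark is more than 5% weight loss.
- **Definition.** Section 3 gives one definition: "We will estimate PWR as the difference in measured weight at post-intervention and self-reported pre-pregnancy weight". Baseline weight does not enter it. Section 8.1 places the final assessment "immediately after completion of the intervention (Week 16".
- **Entry.** Section 5.1 states that "an individual must meet all of the following criteria". The only weight-related item of the eight begins "Has a body mass index" and sets a floor on current BMI (above 25 kg/m² there, at least 25 in the synopsis and Section 5). No item uses pre-pregnancy or retained weight. The three exclusions in Section 5.2 cover weight-affecting medication, current or planned pregnancy, and "participating in another weight loss intervention".
- **Analysis.** Section 9.4.2 says "we will calculate point estimates and confidence intervals for change in weight and PWR". Section 9.3 says "For secondary outcomes, we will include all randomized participants (i.e., intention-to-treat". Section 9.1 rules out formal hypothesis testing.
- **Use.** Sections 3 and 9.4.2 name the weight measures as the intended primary outcome of the larger trial.

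**The concern.** A success benchmark for preliminary efficacy should be hard to reach unless something changes between baseline and Week 16. This one is a level at a single time, and nothing in the entry criteria keeps that level above the threshold at the start. A woman whose BMI was already in range before pregnancy can enroll with little or no retained weight. She then satisfies the benchmark on day 1, in either arm.

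At stake is how the pilot result is read. If the sponsor reports that the PWR benchmark was met, that statement may reflect who was enrolled and not what the intervention did. Because PWR is meant to carry forward to the larger trial, a reader planning that trial could take it as an encouraging signal when it is partly a description of case mix.

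**Working it through.** **The plan's own figure.** The plan states no number for PWR beyond the 5 kg threshold. Its only precision figures (Section 9.2) are 95% confidence interval widths of 0.31 for n = 40 and 0.44 for n = 20. They reproduce as Wald widths at p = 0.5: 2 × 1.96 × √(0.25/40) = 0.310 and 2 × 1.96 × √(0.25/20) = 0.438. They do not bear on the benchmark itself, but they matter for one possible remedy, discussed under the objection.

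**Step 1: the algebra (no assumption needed).** Let P be pre-pregnancy weight, W0 baseline weight and W16 Week 16 weight.
- Baseline PWR: b = W0 − P.
- Week 16 PWR: W16 − P = b + (W16 − W0).
- The benchmark is met when b + (W16 − W0) < 5, that is, when weight change is below 5 − b.

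If b < 5, the right-hand side is positive. Zero change meets the benchmark, and so does any gain smaller than 5 − b kg. Replacing each quantity by its group mean gives the same result: an arm with mean baseline PWR of 3 kg and a mean gain of 1 kg has a Week 16 mean of 4 kg and meets it.

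**Step 2: two illustrative participants (invented weights).**

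| | Pre-pregnancy | Baseline | Week 16 | Weight change | PWR, baseline to Week 16 | < 5 kg | > 5% loss |
|---|---|---|---|---|---|---|---|
| A | 80 kg | 82 kg | 84 kg | +2 kg (+2.4%) | 2 to 4 kg | met | not met |
| B | 80 kg | 95 kg | 87 kg | −8 kg (8/95 = 8.4% loss) | 15 to 7 kg | not met | met |

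Participant A satisfies the BMI criterion at any height below √(82/25) ≈ 1.81 m.

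**Step 3: how many could be affected.** The documents give neither a mean nor an SD for baseline PWR, so this step rests on assumed values. With b normal and SD 6 kg, the share below 5 kg at entry is Φ((5 − mean)/6):
- mean 3 kg: Φ(0.33) = 0.63
- mean 5 kg: Φ(0) = 0.50
- mean 8 kg: Φ(−0.50) = 0.31

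Over a wider assumed grid (mean 2 to 8 kg, SD 4 to 8 kg) the share runs from 23% (mean 8, SD 4) to 77% (mean 2, SD 4), or about 5 to 15 of the 20 participants per arm.

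**Step 4: no effect at all.** Add an assumed 16-week weight change with mean 0 and SD 3 kg, independent of b. Across the same grid, 27% to 73% would meet the benchmark at Week 16. Of those, 20% to 42% would have gained weight.

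**The case against.** **The trial is randomized.** Baseline PWR is balanced between arms in expectation, and Section 9.3 keeps everyone randomized. A difference between arms in Week 16 PWR, or in the share below 5 kg, is informative. This stands. A reader might infer that PWR in this trial says nothing about preliminary efficacy; the documents do not support that. The gap is narrower: the benchmark is written as an absolute level and is not tied to the control arm.

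**No PWR responder rate is planned.** Also true. A reader might infer that a responder rate driven by case mix will be carried into the larger trial's planning. No section plans one, and what Section 9.2 sends forward is the variability of change in weight and behaviors. The table leaves open whether the benchmark is per participant or a group mean. By Step 1 the weakness is present under both readings.

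**The planned analysis may already be a change.** The phrase in Section 9.4.2 can be read as change in PWR. Pre-pregnancy weight then cancels, so change in PWR in kg equals change in weight in kg, and entry level no longer matters. But a threshold of 5 kg on that quantity would not describe retention, and Section 3 defines only the Week 16 level. The wording needs settling either way.

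**A level and a change are different constructs.** Participants A and B might suggest that the plan ranks people in the wrong order. That goes too far. Retention is legitimately a level, Section 2.3.3 speaks of preventing it, and the weight-loss benchmark classifies both participants sensibly. The example shows only that the retention benchmark cannot stand alone.

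**Restricting the benchmark to those with 5 kg or more retained at entry is costly.** Under the 63% to 31% shares above, 20 × 0.37 to 20 × 0.69, or about 7 to 14 per arm, would remain before attrition. The Wald width at p = 0.5 would be 1.96/√7 = 0.74 to 1.96/√14 = 0.52, against the planned 0.44. It would also depart from the all-randomized population. This stands, and the fix below does not require it.

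**Conclusion.** The point holds in limited form. The benchmark can be met at enrolment, and still be met after weight gain, because it is an absolute Week 16 level and entry sets no minimum retained weight. That conclusion follows from the plan's own definitions and rests on no assumption. Meeting the benchmark is therefore not, on its own, evidence of preliminary efficacy.

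How many participants this touches cannot be derived from the documents. The 31% to 63% range assumes a normal baseline PWR with SD 6 kg and means of 8 down to 3 kg; it shows that the share could be substantial, not what it is.

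The consequence is modest. This is one secondary, descriptive benchmark in a feasibility pilot without hypothesis testing. The feasibility and acceptability outcomes, the weight-loss benchmark and a between-arm comparison are unaffected. It is worth correcting because the correction costs almost nothing.

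**What to change.** In Sections 3 and 9.4.2:

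1. Record self-reported pre-pregnancy weight once, before randomization, and compute PWR at baseline and at Week 16 from that same value.
2. In all randomized participants, report by arm the share below 5 kg at baseline and at Week 16, as a shift table (below 5 kg; 5 kg or more).
3. Report the between-arm difference in Week 16 PWR, adjusted for baseline PWR. Give 95% confidence intervals for the estimates in items 2 and 3.
4. State that the 5 kg benchmark is interpreted against the baseline share and the control arm, and is not a stand-alone success criterion.
5. Optionally, show results among those with PWR of 5 kg or more at baseline, as description only.

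**Cost.** Baseline weight is already measured (Section 1.3). The documents do not say when pre-pregnancy weight is asked, so the change is one baseline item if it is not already collected then, plus a little more analysis. No change to visits, sample size or intervention is needed.
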